9.1.3 Definition of an Adverse Event

An AE is any untoward medical occurrence in a patient administered a medicinal or nutritional product (including infant and toddler formulas [hereinafter "pediatric formulas"]) or medical device. The event need not necessarily have a causal relationship with the product treatment or usage. Examples of adverse events include but are not limited to:

- Abnormal test findings;
- Clinically significant symptoms and signs;
- Changes in physical examination findings;
- Hypersensitivity;
- Lack of efficacy;
- Drug abuse;

- Drug dependency.

Additionally, for medicinal products, they may include the signs or symptoms resulting from:

- Drug overdose;
- Drug withdrawal;
- Drug misuse;
- Off-label use;
- Drug interactions;
- Extravasation;
- Exposure during pregnancy;
- Exposure during breast feeding;
- Medication error;
- Occupational exposure.

9.1.4 Hemophilia Events

Hemophilia events are a subset of AEs that are related to the condition of hemophilia or are directly the consequences of bleeding events. Hemophilia events that require hospitalizations or meet other SAE criteria (defined below) should be reported as SAEs. If there is any doubt whether the information constitutes an AE, the information is treated as an AE for the purposes of this protocol.

9.1.5 Abnormal Test Findings

The criteria for determining whether an abnormal objective test finding should be reported as an adverse event are as follows:

- Test result is associated with accompanying symptoms, and/or
- Test result requires additional diagnostic testing or medical/surgical intervention, and/or
- Test result leads to a change in study dosing or discontinuation from the study, significant additional concomitant drug treatment, or other therapy, and/or
- Test result is considered to be an adverse event by the investigator or sponsor.

Merely repeating an abnormal test, in the absence of any of the above conditions, does not constitute an adverse event. Any abnormal test result that is determined to be an error does not require reporting as an adverse event.

9.2 Serious Adverse Events

A serious adverse event is any untoward medical occurrence in a patient administered a medicinal or nutritional product (including pediatric formulas) at any dose that:

- Results in death;
- Is life-threatening;
- Requires inpatient hospitalization or prolongation of hospitalization;
- Results in persistent or significant disability/incapacity (substantial disruption of the ability to conduct normal life functions);
- Results in congenital anomaly/birth defect.

Lack of efficacy should be reported as an adverse event when it is associated with a serious adverse event.

Medical and scientific judgment is exercised in determining whether an event is an important medical event. An important medical event may not be immediately life-threatening and/or result in death or hospitalization. However, if it is determined that the event may jeopardize the patient or may require intervention to prevent one of the other outcomes listed in the definition above, the important medical event should be reported as serious.

Examples of such events are intensive treatment in an emergency room or at home for allergic bronchospasm; blood dyscrasias or convulsions that do not result in hospitalization; or development of drug dependency or drug abuse.

Additionally, any suspected transmission via a Pfizer product of an infectious agent, pathogenic or non-pathogenic, is considered serious. The event may be suspected from clinical symptoms or laboratory findings indicating an infection in a patient exposed to a Pfizer product. The terms “suspected transmission” and “transmission” are considered synonymous. These cases are considered unexpected and handled as serious expedited cases by PV personnel. Such cases are also considered for reporting as product defects, if appropriate.

The following events must be considered medically important and have the same reporting requirements as SAEs:

- FIX inhibitor development
- FIX hypersensitivity allergic reaction
- Thrombogenicity

- Lack of effect
- Red blood cell agglutination

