Investigator	A person, with the appropriate qualifications, responsible for the conduct of the registry at a study site.
Lack of Efficacy/Lack of Effect	Lack of efficacy/effect is the failure of expected pharmacologic action or therapeutic benefit.
MTP	Patients who have received at least one ED but less than or equal to 150 documented prior Factor IX EDs (≤ 150 EDs).
On-demand treatment	Treatment of hemorrhages, as needed, by administering an unscheduled bolus infusion of BeneFIX to stop bleeding and control hemostasis.
Preventive treatment	Factor IX replacement therapy given before an event that could increase the risk of bleeding (e.g. surgery or exercise).
Prophylaxis	Factor IX replacement therapy administered at a routine interval such as every other day, for a prolonged period of time, to prevent occurrence of spontaneous bleeding episodes.
Prothrombin Complex Concentrates	Produced from the cryoprecipitate supernatant of plasma pools after removal of antithrombin and factor XI. Depending on the processing technique, PCCs may contain clotting factors II, IX, X and sometimes VII. To prevent activation of these factors, most PCC contain heparin. PCC may also contain the natural coagulation inhibitors protein C and protein S.
PTP	Patients who have received more than 100 documented prior Factor IX EDs (>150 EDs).
PUP	Patients who have not received any Factor IX products
Registry start date	Date the first registry subject provides informed consent.
Registry end date	Date of last contact with the last subject on the registry.
Regulation	The term regulation refers to all applicable regulations, laws, and guidelines. The regulations may be international, national, or local and may include but are not limited to the Code of Federal Regulations (United States); the European Clinical Trials Directive; the

	International Conference on Harmonisation (ICH) Guideline for Good Clinical Practice; and the World Medical Association Declaration of Helsinki: Ethical Principles for Medical Research Involving Human Subjects.
Treatment Period	Day 0 until study completion/withdrawal

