7.4.3 Safety Data Collection (Day 0 to 12 months/Early Withdrawal)

Safety data collected throughout the treatment period (Day 0 to 12 months/Early Withdrawal) will consist of:

- All AE and SAE data, including product-related medically important adverse events (inhibitor development, FIX hypersensitivity allergic reactions, thrombogenicity, lack of effect and red cell agglutination,). This data will be reported on the appropriate CRF and AEM forms during treatment with BeneFIX.

- Laboratory results determining the presence of FIX inhibitor antibodies by the Bethesda assay or Nijmegen modification of the Bethesda assay are recommended to be collected for subjects at all study visits.
- Changes in concomitant diseases or medicinal therapy
 1. Medicinal concomitant therapy
- FIX activity and recovery values, if available and assessed at routine clinic visits.

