7.8. Data analysis

Detailed methodology for summary and statistical analyses of data collected in this study will be documented in a Statistical Analysis Plan (SAP), which will be dated, filed and maintained by the sponsor. The SAP may modify the plans outlined in the protocol; any major modifications of primary endpoint definitions or their analyses would be reflected in a protocol amendment.

A statistical sample size calculation will not be performed for this study. Because all eligible and willing-to-participate subjects will be enrolled in the study and no statistical hypotheses are tested.

All safety and efficacy analyses, except the analysis for Annualized Bleeding Rates (ABR), will be performed on all subjects who receive at least one dose of BeneFIX. ABR analysis will be performed on subjects who participated in prophylaxis period for at least 6 months.

The primary safety outcomes to be reported will be development of clinically significant FIX inhibitors, FIX hypersensitivity allergic reactions, thrombogenicity, lack of effect and red cell agglutination.

Secondary safety outcomes include the frequency of adverse events and serious adverse events, etc.

Secondary efficacy outcomes will be:

- Annualized bleeding rates (ABR) in subjects receiving treatment with BeneFIX,
- The responses to all on-demand treatment with BeneFIX for all bleeds (4 point scale of assessment),
- Number of BeneFIX infusions to treat each new bleed,
- Number of spontaneous/non traumatic breakthrough bleeds within 48 hours of a prophylaxis dose of BeneFIX.

The efficacy results of this study will be presented using descriptive statistics. The following descriptive statistics will be used:

- For numeric endpoints: sample size, mean, standard deviation, median, minimum and maximum;
- For categorical endpoints: count and percentage.

Safety data will be tabulated and listed according to Pfizer's standard reporting algorithms. The reasons for discontinuation of BeneFIX therapy will be described.

Subgroup analysis will be done by several sub-populations.

Additional details of the analysis will be provided in the statistical analysis plan and/or the clinical study report. This information may include details of missing and, if applicable, unused and spurious data. Deviations from the statistical plan will be reported in the clinical study report.

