9 MANAGEMENT AND REPORTING OF ADVERSE EVENTS/ADVERSE REACTIONS

9.1 Adverse Event Reporting

9.1.1 Adverse Events

All observed or volunteered adverse events regardless of treatment group (if applicable) or suspected causal relationship to BeneFIX will be recorded on the adverse event page(s) of the case report form (CRF) as follows.

For all adverse events, the investigator must pursue and obtain information adequate both to determine the outcome of the adverse event and to assess whether it meets the criteria for classification as a serious adverse event (see section "Serious Adverse Events") requiring immediate notification to Pfizer or a Pfizer-designated representative. For all adverse events, sufficient information should be obtained by the investigator to determine the causality of the adverse event. The investigator is required to assess causality. For adverse events with a causal relationship to BeneFIX follow-up by the investigator is required until the event or its sequelae resolve or stabilize at a level acceptable to the investigator, and Pfizer concurs with that assessment.

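### Section 9.2 gives two conflicting reporting rules for lack of efficacy/effect, which is a primary safety outcome

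*Protocol*

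**What the plan says.** Section 7.8 names lack of effect among the primary outcomes: "primary safety outcomes to be reported will be development of clinically significant FIX inhibitors, FIX hypersensitivity allergic reactions, thrombogenicity, lack of effect", followed by red cell agglutination. The table of terms in section 1 has one entry for both names: "Lack of efficacy/effect is the failure of expected pharmacologic action or therapeutic benefit".

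Section 9.2 then contains two instructions. The first is conditional: "Lack of efficacy should be reported as an adverse event when it is associated with a serious adverse event". The second closes the section: "The following events must be considered medically important and have the same reporting requirements as SAEs". Lack of effect is one of the five events listed under it, and no accompanying SAE is required.

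Three other places bear on the same event. Section 9.1.3 gives "Lack of efficacy" as an example of an adverse event, without qualification. Section 9.1.1 says: "All observed or volunteered adverse events regardless of treatment group (if applicable) or suspected causal relationship to BeneFIX will be recorded". Section 7.4.3 collects "All AE and SAE data, including product-related medically important adverse events (inhibitor development, FIX hypersensitivity allergic reactions, thrombogenicity, lack of effect", again without condition.

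**The concern.** Two rules for one event become a problem when the event is a primary outcome. Section 7.8 tests no hypothesis and plans descriptive summaries, so the reported counts are themselves the study result.

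The denominator in section 7.8 is all subjects with at least one dose. A subject whose event goes unreported therefore stays in the denominator and drops out of the numerator. If some sites follow the conditional sentence as a limit and others follow the list, the pooled lack-of-effect figure mixes two ascertainment rules. Differences between sites could then reflect how section 9.2 was read and not how the product performed.

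**Working it through.** No arithmetic in the protocol bears on this point: it states no sample size, expected event rate or power. The check is a comparison of the provisions for one test case, a lack-of-effect event with no accompanying SAE.

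| Protocol section | Rule | Result for the test case |
|---|---|---|
| 1 (terms) | One definition for both names | The two rules in 9.2 cannot be assigned to different events |
| 7.4.3 | Collected among the medically important adverse events | Captured |
| 7.8 | Primary safety outcome | Should be counted |
| 9.1.1 | All observed or volunteered adverse events recorded | Captured |
| 9.1.3 | Lack of efficacy is an example of an adverse event | Is an adverse event |
| 9.2, conditional sentence | Report as an adverse event when associated with an SAE | Not addressed or, read as a restriction, not reported |
| 9.2, closing list | Same reporting requirements as an SAE | Reported; under 9.3.1, within 24 hours of awareness |

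1. *Event accompanied by an SAE.* Both rules in 9.2 lead to a report, so no event is lost.
2. *Event without an SAE.* The closing list requires a report at SAE level. The conditional sentence is either silent or points the other way.
3. *What the condition does.* Section 9.1.3 already makes lack of efficacy an adverse event in general. A sentence saying that it should be reported as one in a particular circumstance adds nothing unless it narrows that general position. This makes the restrictive reading plausible, although the sentence does not state it.
4. *Size.* Let r be the share of lack-of-effect events arising at sites that read the sentence as a restriction, and q the share of those events that accompany an SAE. The fraction of events lost is r × (1 − q). The protocol gives neither r nor q. The result is 0 if r = 0 or q = 1, and 1 if r = 1 and q = 0. The documents do not narrow that range.

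**The case against.** The strongest reply is that the protocol, read whole, already requires capture. The conditional sentence says *should* and *when*; it does not say *only when* and tells no one to leave anything out. The closing list says *must*, names lack of effect and stands in the same section. Sections 7.4.3, 9.1.1 and 9.1.3 point the same way, and section 9.1.4 resolves doubt towards treating information as an adverse event. A site loses events only if it reads one sentence narrowly and overlooks the rest.

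Most of this stands. A reader might infer that section 9.2 as written suppresses the primary count. The documents do not support that, because the mandatory list requires the very reports said to be suppressed.

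The reply does not dispose of the contradiction. The conditional sentence is the only one that addresses when lack of efficacy is reported as an adverse event, so a site may take it as the specific rule that qualifies the general ones. The doubt provision sits under hemophilia events, and does not help a site that finds the sentence clear. The weight of the text shows which reading was probably intended, but the conflicting instruction is still there.

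A reader might also infer that the inhibitor outcome is reduced, since the section 1 definition of a clinically significant inhibitor mentions events indicating decreased efficacy. That is not shown. The definition has a second, separate criterion (alternate hemostatic products, or an increased dose or dosing frequency), and inhibitor development is itself on the mandatory list.

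**Conclusion.** The point holds as an internal contradiction that bears on a primary outcome. Section 9.2 gives a conditional and an unconditional reporting rule for an event that section 1 defines once. The unconditional rule is the stronger and is supported elsewhere, so the supportable conclusion is a risk of uneven reporting between sites. A certain under-count is not established.

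The risk rests on one assumption: that at least some sites read the conditional sentence as a restriction. The loss could be nil if every site follows the closing list. Any percentage put on it would be an invented figure.

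A reader might go further and ask for a lack-of-effect variable derived from the diary response scale and the 48-hour breakthrough bleeds. The documents do not make that necessary. Both items are already secondary efficacy outcomes in section 7.8, such a variable would introduce an event definition that the protocol does not use, and operational detail of this kind can sit in the statistical analysis plan.

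**What to change.** Delete the conditional sentence in section 9.2, or reword it, so that the protocol carries one reporting rule for lack of efficacy/effect. That rule should agree with the primary outcome in section 7.8, with sections 7.4.3 and 9.1.3, and with the closing list in 9.2. Using one of the two names throughout would help. The change is best made before enrollment, because events never reported as adverse events may not be recoverable for the investigator-reported count.

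The cost is an edit to one sentence, with no new data collection. Slightly more events may need processing, and the reported lack-of-effect percentage may be higher than it would be if some sites applied the restrictive reading.

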9.2.1 Hospitalization

Adverse events reported from studies associated with hospitalization or prolongation of hospitalization are considered serious. Any initial admission (even if less than 24 hours) to a healthcare facility meets these criteria. Admission also includes transfer within the hospital to an acute/intensive care unit (eg, from the psychiatric wing to a medical floor, medical floor to a coronary care unit, neurological floor to a tuberculosis unit).

Hospitalization in the absence of a medical AE is not in itself an AE and is not reportable. For example, the following reports of hospitalization without a medical AE are not to be reported.

- Social admission (e.g., patient has no place to sleep)
- Administrative admission (e.g., for yearly exam)
- Optional admission not associated with a precipitating medical AE (e.g., for elective cosmetic surgery)
- Hospitalization for observation without a medical AE
- Admission for treatment of a pre-existing condition not associated with the development of a new AE or with a worsening of the pre-existing condition (e.g., for work-up of persistent pre-treatment lab abnormality)
- Protocol-specified admission during clinical study (e.g., for a procedure required by the study protocol)

9.2.2 Causality Assessment

The investigator's assessment of causality must be provided for all adverse events (serious and non-serious). The investigator must record the causal relationship in the CRF, as appropriate, and report such an assessment in accordance with the serious adverse reporting requirements if applicable.

An investigator's causality assessment is the determination of whether there exists a reasonable possibility that BeneFIX caused or contributed to an adverse event. If the investigator's final determination of causality is unknown and the investigator does not know whether BeneFIX caused the event, then the event will be handled as related to BeneFIX for reporting purposes. If the investigator's causality assessment is unknown but not related to BeneFIX this should be clearly documented in the CRF.

9.2.3 Exposure During Pregnancy

An exposure during pregnancy (also referred to as exposure in-utero [EIU]) occurs if:

1. A female becomes, or is found to be, pregnant either while receiving or having been exposed to (eg, environmental) BeneFIX or the female becomes, or is found to be, pregnant after discontinuing and/or being exposed to BeneFIX (maternal exposure).
2. A male has been exposed, either due to treatment or environmental exposure to BeneFIX prior to or around the time of conception and/or is exposed during the partner pregnancy (paternal exposure).

As a general rule, prospective and retrospective exposure during pregnancy reports from any source are reportable irrespective of the presence of an associated AE/SAE.

An example of environmental exposure would be a case involving direct contact with a Pfizer product in a pregnant woman (e.g., a nurse reports that she is pregnant and has been exposed to chemotherapeutic products).

If a study patient or study patient's partner becomes, or is found to be, pregnant during the study patient's treatment with BeneFIX the investigator must submit this information to Pfizer within 24 hours of awareness of the pregnancy, irrespective of whether an adverse event has occurred.

Follow-up is conducted to obtain pregnancy outcome information on all Exposure in Utero reports with an unknown outcome. The investigator will follow the pregnancy until completion or until pregnancy termination (eg, induced abortion) and then notify Pfizer of the outcome. The investigator will provide this information as a follow up to the initial Exposure in Utero report.

For clinical studies conducted in pregnant women, data on the pregnancy outcome and non-serious AEs are expected to be collected and analyzed in the clinical database. In such instances only EIUs associated with a SAE are to be reported.

9.2.4 Medication Error

A medication error is any unintentional error in the prescribing, dispensing or administration of a medicinal product that may cause or lead to inappropriate medication use or patient harm while in the control of the health care professional, patient, or consumer. Such events may be related to professional practice, health care products, procedures, and systems including: prescribing; order communication; product labeling, packaging, and nomenclature; compounding; dispensing; distribution; administration; education; monitoring; and use.

Medication errors include:

- Near misses, involving or not involving a patient directly (eg, inadvertent/erroneous administration, which is the accidental use of a product outside of labeling or prescription on the part of the healthcare provider or the patient/consumer);
- Confusion with regard to invented name (eg, trade name, brand name).

The investigator must submit the following medication errors to Pfizer within 24 hours of awareness, irrespective of the presence of an associated AE/SAE :

- Medication errors involving patient exposure to the product, whether or not the medication error is accompanied by an AE.
- Medication errors that do not involve a patient directly (eg, potential medication errors or near misses). When a medication error does not involve patient exposure to the product the following minimum criteria constitute a medication error report:
 - An identifiable reporter;
 - A suspect product;
 - The event medication error.

9.3 Reporting Requirements

Each adverse event is to be assessed to determine if it meets the criteria for serious adverse events.

If a serious adverse event occurs, expedited reporting will follow local and international regulations, as appropriate.

9.3.1 Serious Adverse Event Reporting Requirements

If a serious adverse event occurs, Pfizer is to be notified within 24 hours of awareness of the event by the investigator. In particular, if the serious adverse event is fatal or life-threatening, notification to Pfizer must be made immediately, irrespective of the extent of available adverse event information. This timeframe also applies to additional new information (follow-up) on previously forwarded serious adverse event reports as well as to the initial and follow-up reporting of exposure during pregnancy, exposure during breast feeding and medication error cases.

In the rare event that the investigator does not become aware of the occurrence of a serious adverse event immediately (eg, if an outpatient study patient initially seeks treatment elsewhere), the investigator is to report the event within 24 hours after learning of it and document the time of his/her first awareness of the adverse event.

For all serious adverse events, the investigator is obligated to pursue and provide information to Pfizer in accordance with the timeframes for reporting specified above. In addition, an investigator may be requested by Pfizer to obtain specific additional follow-up information in an expedited fashion. This information collected for serious adverse events is more detailed than that captured on the adverse event case report form. In general, this will include a description of the adverse event in sufficient detail to allow for a complete medical assessment of the case and independent determination of possible causality. Information on other possible causes of the event, such as concomitant medications and illnesses must be provided. In the case of a patient

death, a summary of available autopsy findings must be submitted as soon as possible to Pfizer or its designated representative.

